4.2. Theory of Change

4.3. Intervention Dates

The intervention will be delivered to participants over an eight month time period beginning in August 2024.

Table 5: TIDieR Framework²

Name	Personalised Budgets Randomised Controlled Trial
Why	Poverty and low income are major contributors to people's risk of homelessness, and their inability to escape homelessness and its consequences. There is therefore an argument for more financial support being given to people experiencing homelessness as a mechanism to remove some (although not all) of these barriers. Those in favour of personalised budgets would also argue that financial support given could be more beneficial if it is also accompanied with support in deciding what to spend it on to achieve the best outcomes possible. This might also mitigate some potential risks for the group, given that some people experiencing homelessness could be at risk of exploitation. The Greater Change personalised budgets intervention therefore works with people with experiences of rough sleeping who are currently in temporary accommodation, and with a charity worker who supports them, to identify a concrete need that a personalised budget can be spent on. This helps to ensure that the money is spent in a way that maximises benefit to the recipient, and that the risk of harm is significantly reduced.
Who (recipients)	People who are currently housed in temporary accommodation, with experience of rough sleeping. Participants will be 18+ and have an existing relationship with a caseworker from an eligible charity partner. Charity partners are eligible if they work with people in temporary accommodation, and if they do not currently provide substantial financial support (the modal £100 interval provided by any existing financial support scheme is less than £400).
What (materials)	A payment of a specified amount agreed between Greater Change, the participant and their caseworker, provided to the caseworker to make the purchases agreed. The amount provided, and what it is spent on, will vary. Average value of goods/services provided with the personalised budget is expected to be around £4,000, with a minimum budget of £2000 and a 'soft' maximum of £5,000 (which can be exceeded in exceptional cases as judged by Greater Change).
What (procedures)	Participants are referred to Greater Change via a referral form. A discussion takes place between the caseworker, Greater Change, and the participant to decide the best use of the personalised budget. When this is agreed, Greater Change will transfer the budget to the partner charity within 4 weeks, who will spend the money as agreed.
Who (provider)	The intervention will be delivered by Greater Change, in partnership with charity partners.
	•

-

² BMJ 2014;348:g1687; doi: https://doi.org/10.1136/bmj.g1687

How (format)	Money agreed will be transferred to the charity partner's bank account and used to purchase what was agreed.		
Where (location)	Across England: South West (Second Step), South East (Porchlight, Gravesham Council), London (Centre Point Soho, Depaul UK, Your Place, Islington Council) Cambridge (Cambridge Cyrenians), East Midlands (Action Homeless), Leeds (Turning Lives Around)		
When and how much (dosage)	Payments will be made within 4 weeks of being agreed. It is anticipated that average payments will be around £4,000, but they may exceed this where necessary.		
	Participants are expected to spend their allocated funds within a three-month period. However, on a case-by-case basis, participants may receive extensions to ensure they can spend the funding as needed.		
Tailoring	Greater Change instructs charity partners to centre the personalised budget planning conversation around the participant's individual aspirations, goals and requirements and prompts caseworkers to afford their clients the dignity to make their own decisions. The decisions about spending are tailored to the individual circumstances of the participant, and are agreed upon by the charity partner; the participant; and Greater Change.		
Control condition	Control participants, as with treatment-arm participants, continue to be able to access all other support that they are entitled to (e.g. Universal Credit, rent assistance) and will not have been informed about the quantum of the personalised budget they could have received but have not due to their group allocation. This means, that control participants will not be allocated a personalised budget but are entitled to all otherwise available support.		

5. IMPACT EVALUATION

5.1. Aims, Objectives and Hypotheses

Aims

This impact evaluation aims to understand the impact that the Greater Change personalised budgets intervention has on housing stability and perceived housing quality and satisfaction, financial stability, subjective wellbeing, life satisfaction, and employment outcomes, measured at baseline, six and twelve months after randomisation using a randomised controlled trial design.

Objectives

Primary objective

The primary objective of the trial is to quantify the effects of providing a personalised budget for financial assistance given to participants who have experience of sleeping rough and are currently housed in temporary accommodation on their housing stability and perceived housing quality and satisfaction.

Secondary objective(s)

The secondary objective is to quantify the impact of the personalised budget intervention on financial stability; wellbeing; life satisfaction; and employment.

Research Hypotheses

Primary hypothesis

Receiving the intervention will:

 Improve housing stability and perceived housing quality and satisfaction

Secondary objective(s)

Receiving the intervention will lead to:

- 2. Improved financial stability
- 3. Improved wellbeing and life satisfaction
- 4. No decrease but perhaps an increase in employment

5.2. Study Design

Study design details

This trial is a parallel randomised controlled trial with randomisation at the level of the individual participant and with data collection at three time points. Randomisation will occur on a 1:1 ratio, with stratification at the level of the charity partner.

Allocation

Randomisation will be conducted by IFF. IFF Research's approach to randomisation for the two-arm RCTs is 1:1 randomisation at the individual level. This will offer the most reliable estimates because, at the point of randomisation, all important factors would be balanced across the intervention and control condition and the effects can be securely attributed to the trial, within standard statistical tolerances.

To account for rolling participant recruitment to the trial, IFF will use a sequential individual randomisation stratified by charity partner, and with blocks of four samples in each block. In each block of four participants, two would be randomly allocated to the treatment group and two would be randomly allocated to the control group. Since we

do not know the exact number of trial participants, and this is subject to change, we do not know how many blocks we will end up with in the trial. The randomisation algorithm is coded into the baseline survey script; participants will be automatically randomised upon submission of the survey.

Once participants are randomised, we will download the data and check that the randomisation has worked as it should statistically. We will then send through the list of unique IDs that have been assigned to each group to Greater Change, so they know who to deliver the treatment to. Greater Change will then inform the charity partner and the charity partner will inform the participants themselves.

Intervention

After being referred by partner charities, participants allocated to treatment will get support from caseworkers to decide on a plan for them to stop them experiencing homelessness. The caseworker and the client define together what they need (e.g. work tools, driver's licence or secure a deposit), and the amount needed (£4,000 on average). When the funds are made available, the caseworker is responsible for purchasing what was defined in the client's plan.

The organisation delivering the model is Greater Change. They work together with local partner charities to ensure that clients receive additional non-financial support alongside funding in a timely manner. In contrast to other conditional funds, Greater Change does not have pre-set eligibility and spending criteria. The conditional funds are used to support the flexible and sustainable plan created and agreed upon ahead of time by the support worker and the service user.

This project will compare the use of personalised budgets that are managed by a caseworker and control groups under business-as-usual.

We assume that, on average, participants in the treatment group will receive funds of £4,000.

Participants are expected to spend their allocated funds within a three-month period. However, on a case-by-case basis, participants will be permitted to receive the intervention even in the face of necessary spending extensions, these cases will not be treated as non-compliant nor excluded from analysis. These extensions are in response to operational realities and are critical to the successful running of the trial. They also enable the intervention to more closely reflect how it would operate outside a trial context. The reasons for granting extensions can be grouped into two categories:

- Staff-related delays: including administrative expenditure delays, annual leave of case workers, and reduced partner engagement with participants.
- Participant-related delays: including hospitalisation, rehabilitation, custody, bereavement, or other extenuating personal circumstances.

Control

Participants will retain the same support as they would otherwise have received, including access to smaller personalised budgets or grants, as they would have had in the absence of the trial.

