This RCT will be consent-randomised. This means that only those who consent to participate in the research will be randomised to either receive the personalised budget or not. This is a common type of RCT where the intervention is not current practice, and where there are limited resources available to provide the intervention. The implementation of personalised budgets in the proposed settings and locations is not something that is currently available - it is being made available for the purpose of the research project. This means that individuals who don't participate in the research will not have an existing benefit withheld, and will continue to receive all the support and care, including other financial assistance, for which they are eligible. In the model's current form, Greater Change personalised budgets average around £1,200 and are paid out in less than two weeks time. Outside of the present trial, Greater Change furthermore makes this accessible more broadly to recipients who are interacting with any kind of homelessness service (i.e. due to being at risk of homelessness, experiencing or having experienced homelessness in the recent past). Otherwise, all Greater Change mechanisms tested here are the same as they would be if this program were to be scaled up. For the purpose of the present trial, prospective participants will be identified by local charity partners and enrolled, following which randomisation will occur. Acting as gatekeepers, partnering charity organisations will be thoroughly briefed on the research and they will be given a script to be used by their caseworkers to explain the trial to potential candidates. This script emphasises that individuals are under no pressure to participate if they do not wish to and that doing so will not impact the individual's standing with the delivery partner, or their access to other services and support.

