6.3. Enrolment

Participants will be enrolled in the trial if they consent to do so and provide their baseline data to IFF. We anticipate enrollment starting in August 2024 and continuing for 5 months.

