 transcription. All personal information will be removed from
 transcripts, and transcripts will be stored using the group's
 pseudonymous identifier to link them to the survey responses and
 demographics of the participants. All transcripts will be stored
 securely, and access will be limited to the research team of the
 present study only.

Administrative data from Greater Change and Charity Partners

- Data collection data sources
 We will collect quantitative data from Greater Change and charity partners relating to:
 - The dates on which participants are randomised; funding is agreed, sent to charity partners; and spent by charity partners.
 - The amounts of money being disbursed.
 - What funding is spent on.
 - For the control group, any information held by charity partners on other financial support that they have received (to facilitate dose-response analysis).
- Data collection procedures

Every two months during participant recruitment, we will send a template to each charity partner and to Greater Change with a list of participants assigned to the treatment and control group with their unique identifiers, and ask them to complete the fields for every participant. The researcher assigned to this procedure will not be involved with the final analysis to ensure no bias is introduced.

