- We are conscious that a personalised budget in the region of £4,000 may be considered an undue incentive to participate. We have proposed not to inform participants of the value of the additional financial assistance until they are allocated to the intervention and have provided a briefing for delivery organisations to inform intervention participants, which emphasises that participants do not have to accept the assistance, and reminds them that they can withdraw from the research at any time. In addition, participants will have 2 weeks to consider whether they still wish to participate, before the agreed money is transferred to the charity partner by Greater Change. If they decide to withdraw after the money is transferred or has been spent, they will not have to return the financial assistance or whatever was purchased with it.

Intervention and support

- People experiencing homelessness periodically receive additional finance via support organisations or as a result of Universal Credit back-payments. If they are engaged with a partnering charity organisation, then they receive support to think about how they wish for the funds to be spent, and monitoring to respond to risks of harm arising from receiving a personalised budget. Participants who receive a personalised budget will have more notice that they are receiving it (up to three months) and more support to plan how they would like to use the funds, than they might for other types of finance they might receive. Because the money is not given directly to participants, but is used by charity partners to purchase what has been agreed, this poses less risk to participants than if they received the money directly themselves.
- Partnering charity organisations will ensure that participants are receiving business-as-usual ongoing support throughout the trial period, as well as support around the receipt of the financial assistance, consistent with the delivery partner's service delivery model. Participants will receive this support regardless of whether they decide to withdraw from the research. Administrative data captured from delivery partners will allow us to understand what other financial and material support people will have received, while our interviews with both treatment and control groups will allow us to

identify any differences in the non-personalised budgets support received by the two groups.

Questionnaires and interviews

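### Section 11.2 records other financial support for controls only and states template rounds only during recruitment, so such support cannot be compared between arms or reliably described over 12 months

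*Protocol*

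**What the plan says.** **What participants may receive.** Under the Control heading in section 5.2, controls keep "access to smaller personalised budgets or grants, as they would have had in the absence of the trial". Section 4.1 keeps intervention participants eligible for whatever assistance they can already get and gives both arms equal access to usual support, including financial support. It adds that this equality protects the treatment effect from distortion by differences in access to usual care.

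**What will be recorded.** The administrative data list in section 11.2 contains this item: "For the control group, any information held by charity partners on other financial support that they have received (to facilitate dose-response analysis". On timing, the same section says: "Every two months during participant recruitment, we will send a template to each charity partner and to Greater Change". No later round is stated. Section 6.3 gives the length of recruitment: "We anticipate enrollment starting in August 2024 and continuing for 5 months". The primary outcome in section 7.1 counts days over the 360 days after randomisation.

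**What is promised.** Section 15.4 says: "Administrative data captured from delivery partners will allow us to understand what other financial and material support people will have received". It adds that interviews in both arms will "identify any differences in the non-personalised budgets support received by the two groups". Section 11.2 plans 20 such interviews in total.

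**Related wording.** Section 4.1 says: "The implementation of personalised budgets in the proposed settings and locations is not something that is currently available". It also describes the ordinary offer outside the trial: "Greater Change personalised budgets average around £1,200 and are paid out in less than two weeks time".

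**The concern.** Equal entitlement is not equal receipt. Section 4.1 relies on equal access to keep usual care from distorting the comparison, and it also says caseworkers know which participants have received a budget. Whether other funds in fact reached the two arms equally is an empirical question, and the trial already has the instrument to answer it: a template with one row per participant in both arms (360 rows in Table 8). Section 11.2 narrows the relevant field to one arm and ties the stated rounds to recruitment.

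Three things are lost. The claim in 4.1 cannot be checked. The comparator cannot be described with confidence over the later part of follow-up. And any analysis relating outcome to money received would set a control total that includes other funds against an intervention total that leaves them out.

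**Working it through.** The protocol gives no rate of receipt of other support, so it has no figure of its own on this point to reproduce. Receipt rates below are assumptions.

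**1. Arms covered**

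| Place | Whose other support |
|---|---|
| 4.1 | both arms eligible, equal access |
| 15.4 | people, no arm named |
| 11.2, data sources | control group |
| Table 8 | template rows for both arms |

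Only the data-source item in 11.2 is restricted to one arm. It is also the only place that defines the field.

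**2. Period covered**

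Recruitment is 5 months, so two-monthly rounds give about 2 to 3 rounds. Assume even enrolment at time s between 0 and 5 months, and returns complete up to month L (L of 5 or more). A participant then has L − s months covered, on average L − 2.5.

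- Literal reading, L = 5: average 2.5/12 = 21%; range 0/12 = 0% to 5/12 = 42%.
- Rounds continue until budgets are due to be disbursed (March 2025 in Table 4), L = 8: average 5.5/12 = 46%; range 3/12 = 25% to 8/12 = 67%.

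Neither reading reaches 12 months for anyone. The protocol does not say which applies.

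**3. Error in a dose contrast**

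Suppose a share q in each arm receives other support of amount a. The true contrast is (4,000 + qa) − qa = £4,000. With the item recorded for controls only, the contrast is 4,000 − qa.

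- q = 5%, a = £400 (the bound in Table 5 on the modal amount in partners' existing schemes): 4,000 − 20 = £3,980, low by 0.5%.
- q = 20%, a = £1,200 (the ordinary Greater Change average in 4.1): 4,000 − 240 = £3,760, low by 6%.

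**4. What an unseen imbalance could do**

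Table 7, scenario B, reproduces: (1.960 + 0.842) × √(1 − 0.6²) × √(4/270) = 0.273. As an illustration, let the effect be proportional to pounds, and let a share q of controls receive amount a that the intervention arm does not. The effect becomes 0.273 × (1 − qa/4,000). Power with 135 per arm and residual SD 0.8 is then:

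| a | q = 10% | q = 25% | q = 50% |
|---|---|---|---|
| £400 | 0.79 | 0.78 | 0.76 |
| £1,200 | 0.78 | 0.74 | 0.66 |

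At the scale of partners' own schemes the loss is slight. It becomes material only if sums near £1,200 reach a large share of controls and not the intervention arm. Nothing in the protocol suggests that, but records as specified could not rule it out.

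**The case against.** The strongest reply is that the text should be read for its purpose. The same template must capture when trial funds are agreed, sent and spent. Disbursement runs to March 2025, spending may take three months or longer with extensions (5.2), and the non-compliance rules in 10.6 need final spending data. Stopping in December 2024 would defeat the template, so later returns are likely. This stands: the 21% figure is the literal reading, not an established loss. But a return completed for spending purposes need not cover other support to 12 months, and no round is stated that would.

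Secondly, 11.2 asks for the fields to be completed for every participant. That helps little, because the field itself is defined for controls.

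Thirdly, the definition of a dose-response analysis may sit in an analysis plan not at hand. That is fair as to the model, but no analysis plan can supply data that were not collected for one arm.

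Fourthly, the interviews cover both arms. They are a qualitative sample of 20, useful for explaining differences and not meant to measure them, so it would be wrong either to rely on them for a comparison or to fault their precision.

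A reader might also infer that 4.1 and 5.2 contradict each other on whether controls can receive personalised budgets. The documents do not support that as a substantive conflict. Section 4.1 can be read as meaning the trial budget, and 5.2 the small existing schemes that Table 5 permits at partners. What remains is unclear wording, including silence on whether the ordinary offer of about £1,200 is open to participants during follow-up.

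**Conclusion.** The point holds as a gap in data collection. Section 11.2 is too narrow in arm, and as stated too short in period, to deliver what 15.4 promises or to check what 4.1 asserts. Its direct numerical effect is small: 0.5% to 6% of the £4,000 contrast in a dose-response analysis, assuming equal receipt of 5% at £400 up to 20% at £1,200. Coverage of follow-up averages 21% to 46% depending on how long rounds continue, assuming even enrolment; the protocol does not settle which.

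Two stronger conclusions might be drawn and should not be. One is that the comparator cannot be reported: controls are the arm that is recorded, so it can be described, though perhaps only for the earlier months. The other is that the main result is biased because caseworkers might direct other funds to controls. The protocol gives no sign of this and says allocation will not affect the standard of care. In any case the intention-to-treat estimate remains a valid comparison with usual care as delivered. This is a cheap improvement, not a threat to the primary analysis.

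**What to change.** In section 11.2:

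- Delete the restriction to the control group, so that other financial support is recorded for every participant.
- Add one retrospective round covering the 12 months after each participant's randomisation, sent with the cost spreadsheets that section 12.3 already schedules alongside final data collection.
- Report by arm the share receiving any other grant or budget, and the mean amount.

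As wording only, state in 5.2 that the smaller budgets or grants are usual-care funds other than the trial budget, and say whether Greater Change's ordinary offer is open to participants during follow-up. Nothing need be withheld from controls.

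The cost is one extra field for about 180 intervention rows and one extra template round to Greater Change and the 10 partners listed in Table 5, with no participant contact. Partners can report only what they hold, so the shares will be lower bounds and should be labelled so. Section 13.2 already provides for an addendum before analysis.
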